1 SYNOPSIS

Title: Evaluation of an Updated Dexamethasone Posterior Segment Drug Delivery System Applicator in Participants with Macular Edema due to Retinal Diseases	
Background and Rationale:	
The Dexamethasone Posterior Segment Drug Delivery System is approved for the treatment of macular edema following branch retinal vein occlusion or central retinal vein occlusion, for the treatment of noninfectious uveitis affecting the posterior segment of the eye, and for the treatment of diabetic macular edema.
 
AbbVie is updating the Dexamethasone Posterior Segment Drug Delivery System Applicator to include a change of the implant retention feature, other minor changes to the Dexamethasone Posterior Segment Drug Delivery System Applicator (i.e., change of safety tab color, shortening of the safety tab, linkage hole alignment, lever clasp), as well as the change to the visual/physical depth of penetration feature (needle sleeve).
 
No changes are being made to the Dexamethasone Posterior Segment Drug Delivery System Implant.

Objective(s) and Endpoint(s):	
The primary objective is to demonstrate that the updated Dexamethasone Posterior Segment Drug Delivery System Applicator (that incorporates the final, to-be-marketed design) delivers the Dexamethasone Posterior Segment Drug Delivery System Implant to the vitreous cavity and is suitable for commercial use in patients with macular edema due to retinal diseases.
 
No secondary objective is defined for this study.
 
No primary or secondary efficacy endpoints are defined for this study.
 
The study is not designed to assess efficacy or safety of the study drug. The Dexamethasone Posterior Segment Drug Delivery System Implant is a Food and Drug Administration-approved drug, and its efficacy and safety are already well established.
 
Safety variables that will be evaluated in the study include vital signs, adverse events, and ocular parameters as determined through assessments of best-corrected visual acuity, biomicroscopic slit lamp examination, ophthalmoscopy, and intraocular pressure.
 
The updated Dexamethasone Posterior Segment Drug Delivery System Applicator performance will be assessed via treatment administration assessment form (completed by the investigator) after Dexamethasone Posterior Segment Drug Delivery System Implant administration.
 
Approximately 54 subjects will be enrolled in this study and randomly assigned in a 2:1 ratio to receive the implant using either the updated applicator (test) or the currently-approved applicator (comparator), respectively.

Investigator(s):	Multicenter.
Study Site(s):	Approximately 7 sites in the United States.

Study Population and Number of Subjects to be Enrolled:	Approximately 54 subjects with macular edema due to retinal vein occlusion (branch retinal vein occlusion or central retinal vein occlusion) or diabetic macular edema will be enrolled in the study; subjects will be randomly assigned in a 2:1 ratio to receive the Dexamethasone Posterior Segment Drug Delivery System Implant using either the updated applicator (test) or the currently-approved applicator (comparator), respectively.
Investigational Plan:	This is a Phase 3b, prospective, randomized, open-label, two-arm, 7-day clinical study in subjects with macular edema due to retinal vein occlusion (branch retinal vein occlusion or central retinal vein occlusion) or diabetic macular edema to support the evaluation of the updated Dexamethasone Posterior Segment Drug Delivery System Applicator (that incorporates the final, to be marketed design) and demonstrate that it delivers the Dexamethasone Posterior Segment Drug Delivery System Implant to the vitreous cavity and is suitable for commercial use in patients with macular edema due to retinal diseases.
Key Eligibility Criteria:	Males and females \geq 18 years of age with macular edema due to retinal vein occlusion (branch retinal vein occlusion or central retinal vein occlusion) or diabetic macular edema in the study eye. Subjects with no ocular conditions in the study eye for which Dexamethasone Posterior Segment Drug Delivery System Implant is contraindicated.
Study Drug and Duration of Treatment:	Eligible subjects will receive a single intravitreal administration of Dexamethasone Posterior Segment Drug Delivery System Implant 0.7 mg in the study eye on Day 1 using either the updated Dexamethasone Posterior Segment Drug Delivery System Applicator (that incorporates the final, to-be-marketed design or the currently -approved Dexamethasone Posterior Segment Drug Delivery System Applicator in a ratio of 2:1, respectively.
Date of Protocol Synopsis:	29 November 2021

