2 INTRODUCTION

2.1 Background and Rationale

Why Is This Study Being Conducted?

Dexamethasone Posterior Segment Drug Delivery System (DEX PS DDS) is a Food and Drug Administration (FDA)-approved, biodegradable, NOVADUR® solid polymer drug delivery system containing 0.7 mg of dexamethasone. The DEX PS DDS Implant comes preloaded and is delivered in the vitreous cavity by a single-use DEX PS DDS Applicator with a 22 gauge needle that leaves a sutureless self-sealing wound. The sustained release formulation was designed to release dexamethasone from the DEX PS DDS Implant for up to 6 months into the posterior segment of the eye. The DEX PS DDS is approved for the treatment of macular edema following branch retinal vein occlusion (BRVO) or central retinal vein occlusion (CRVO), for the treatment of noninfectious uveitis affecting the posterior segment of the eye, and for the treatment of diabetic macular edema (DME).

AbbVie is updating the DEX PS DDS Applicator to include a change of the implant retention feature, other minor changes to the DEX PS DDS Applicator (i.e., change of safety tab color, shortening of the safety tab, linkage hole alignment, lever clasp), as well as the change to the visual/physical depth of penetration feature (needle sleeve).

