7. Using sterile technique, open the foil pouch containing the DEX PS DDS Applicator and allow the DEX PS DDS Applicator to gently fall onto the sterile field. Do not drop the DEX PS DDS Applicator onto the field from a great height since that may damage the DEX PS DDS Applicator or dislodge the DEX PS DDS Implant. Remember that only the inside of the foil pouch is sterile.
8. Paint the eyelids, eyelid margins, and lashes of the treated eye 3 times using cotton tip applicators saturated with povidone iodine 5% or local equivalent antiseptic.
9. Place an additional 2 drops of povidone iodine 5% or local equivalent antiseptic on the conjunctiva of the treated eye.

10. If you are using an indirect ophthalmoscope as your coaxial light source, put it on now and adjust it for comfortable viewing. Set it to small pupil (if available) and brightest beam.
11. Put on sterile gloves.
12. Carefully remove the cap by pulling it straight out from the DEX PS DDS Applicator in line with the long axis of the DEX PS DDS Applicator, taking care not to contact the needle with the cap. There is a tube within the cap that closely surrounds the needle, and angling the cap as it is removed can damage the needle or blunt the tip. Inspect the needle tip for damage; the implant retention plug may be visible in the bevel of the updated applicator needle and should not be removed.

Currently-Approved and Updated Applicators:

13. Remove the safety tab from the DEX PS DDS Applicator by pulling it out perpendicular to the long axis of the DEX PS DDS Applicator. Gently place the DEX PS DDS Applicator back on the sterile field taking care to avoid damaging the needle. Do not twist or bend the safety tab to remove it and do not re-cap the DEX PS DDS Applicator.

- If the indirect ophthalmoscope was used for the visualization or if the treating investigator removed the indirect themselves, first re-glove with sterile glove(s), and then remove the safety tab.

- Note: If the safety tab is not removed prior to the injection, it will be extremely difficult if not impossible to depress the actuator button.

14. Apply the sterile drape to the treated eye so that the eyelashes are excluded from the surgical field. If using a non-fenestrated drape, ask the subject to keep his/her eye open as the drape is applied and use the sterile drape scissors to cut a slit in the drape over the treated eye.

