3.13 Treatment Administration Assessment Form

The treatment administration assessment form, as part of the electronic case report form (eCRF), will be completed by the investigator on Day 1 after study drug administration per Section 2.1.

The investigator will evaluate whether the updated (test) or the currently-approved (comparator) DEX PS DDS Applicator dispensed the DEX PS DDS Implant in the vitreous cavity and performed as intended. The position of the DEX PS DDS Implant in the vitreous cavity will be defined¹ as follows:

- Position 1 (P1) = presence of the DEX PS DDS Implant in contact with pars plana and/or ciliary processes.
- Position 2 (P2) = presence of the DEX PS DDS Implant anterior to the equator but with no part of it in contact with pars plana and/or ciliary processes. Equator is identified based on the location of the vortex veins.
- Position 3 (P3) = presence of the DEX PS DDS Implant posterior to the equator. Equator is identified based on the location of the vortex veins.

If the DEX PS DDS Implant is visible between P2 and P3 positions, then it should be marked as P2.

COVID-19 Pandemic-Related Acceptable Protocol Modifications

There are no pandemic or natural disaster-related protocol modifications for the treatment administration assessment form, other than those specified in Section 2.

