4.0 Analysis Populations

The following population sets will be used for the analyses.

The Safety Analysis Set (SAS) consists of all subjects who received DEX PS DDS Implant. Subjects will be included in the analysis according to the updated applicator or currently-approved applicator that was used to deliver the DEX PS DDS Implant.

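### Applicators opened but rejected before injection would be missing from the reported performance: the form follows administration, and product complaints without an adverse event are not due for reporting

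*Protocol*

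**What the plan says.** The sole objective (Protocol 3.1, SAP 2.1) is to show that the updated applicator delivers the implant to the vitreous cavity and is suitable for commercial use. Protocol 3.4 names applicator performance, taken from the treatment administration assessment form, as the endpoint. The Synopsis states that performance "will be assessed via treatment administration assessment form (completed by the investigator) after Dexamethasone Posterior Segment Drug Delivery System Implant administration". Operations Manual 3.13 agrees: the form "will be completed by the investigator on Day 1 after study drug administration". It asks whether the applicator "dispensed the DEX PS DDS Implant in the vitreous cavity and performed as intended".

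The analysis set is limited to subjects who received the implant (Protocol 7.2, SAP 4.0). SAP 4.0 groups them "according to the updated applicator or currently-approved applicator that was used to deliver the DEX PS DDS Implant".

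A defective device also has a second route. Protocol 6.1 counts device damage or malfunction as a product complaint, due in EDC within 24 hours, with a back-up paper form for unassigned product. Operations Manual 4.2 adds photographs, quarantine and a Product Complaint eCRF. Protocol 6.1 then limits the study summary to complaints associated with adverse events; the rest are only monitored.

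Protocol 7.5 says the form will be summarised. The SAP has no section on the form, on applicator performance or on complaints, and its Section 11.0 (Other Analyses) is marked not applicable.

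**The concern.** The article under test is the applicator, and some of its failures can appear before the needle reaches the eye. Protocol 2.1 says: "AbbVie is updating the DEX PS DDS Applicator to include a change of the implant retention feature". It also lists changes to the safety tab. The treatment procedure in Operations Manual 3.12 has several points before injection at which an opened applicator could be set aside. Step 7 warns against letting it fall from a height, an act "that may damage the DEX PS DDS Applicator or dislodge the DEX PS DDS Implant". Step 12 says: "Inspect the needle tip for damage". It adds that a retention plug may be visible in the needle bevel of the updated applicator only. Step 13 removes the safety tab. The manual does not say what follows if a check fails, and neither document has a rule on replacement kits.

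No text calls for a form for a device that is opened and not used, and the analysis set cannot bring that device back in. A device rejected before it touches the eye will seldom have an adverse event attached, so the complaint rule in Protocol 6.1 would normally keep it out of the study summary as well. At stake is whether the evidence on suitability for commercial use covers every applicator opened or only those that reached injection. Because the retention plug is particular to the updated device, rejections before injection could also differ between arms.

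**Working it through.** **1. The plan's own figure.** Protocol 7.8 and SAP 2.4 ask for at least 30 and 15 eyes with about 15% dropout. Updated arm: 30 / (1 − 0.15) = 35.3, rounded up to 36. Approved arm: 15 / 0.85 = 17.6, rounded up to 18. Total: 36 + 18 = 54, as stated. The sample size is not in question; the point concerns which devices enter the denominator.

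**2. Where a rejected applicator goes under the plan.**

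- *A second kit is used.* The subject is treated and is grouped by the device that delivered. The form follows that administration, and nothing requires it to describe the first device.
- *No second kit is used.* The subject receives no implant and is outside the analysis set. SAP 5.0 would count the subject as randomised but not treated, perhaps with a reason, but not as an applicator result.
- *Either way.* A Product Complaint eCRF is due. Unless an adverse event is associated, Protocol 6.1 does not send it to the study summary, and the SAP has no table for it.

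**3. Possible size.** The number of rejected devices, k, is an assumption; the documents give none. Intervals are exact (Clopper-Pearson) 95%. The lower limit is the 0.025 quantile of Beta(x, n − x + 1) and the upper limit is the 0.975 quantile of Beta(x + 1, n − x). For x = n the lower limit is 0.025^(1/n); for 36/36 it is 0.025^(1/36) = 0.903.

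The second column holds 36 treated and delivered, with k further devices opened and rejected: 36 / (36 + k). The third takes 36 randomised, of whom k have the device rejected and receive no second kit: (36 − k) / 36.

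| k | Delivered / opened, 36 treated | Delivered / opened, 36 randomised, no second kit |
|---|---|---|
| 0 | 36/36 = 100% (90.3 to 100) | 36/36 = 100% (90.3 to 100) |
| 1 | 36/37 = 97.3% (85.8 to 99.9) | 35/36 = 97.2% (85.5 to 99.9) |
| 2 | 36/38 = 94.7% (82.3 to 99.4) | 34/36 = 94.4% (81.3 to 99.3) |
| 3 | 36/39 = 92.3% (79.1 to 98.4) | 33/36 = 91.7% (77.5 to 98.2) |

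A tabulation restricted to treated subjects would show 100% in every row, if all of those forms are favourable.

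At the 30-eye minimum the same step gives 30/30 = 100% (lower limit 88.4%), 30/31 = 96.8% (83.3%), 30/32 = 93.8% (79.2%) and 30/33 = 90.9% (75.7%).

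**4. How likely is at least one?** With an assumed rejection rate p per device and 36 devices, the chance is 1 − (1 − p)^36: 30% for p = 1%, 52% for 2%, 84% for 5%. These rates only span a range; nothing in the documents supports one over another.

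**The case against.** The strongest reply is that such devices are already recorded. A product complaint is mandatory, has its own eCRF and a 24-hour limit, and does not depend on an implant having been given. Protocol 2.1 even says that the study's length was set so as to capture complaints linked to administration with the updated applicator. This stands as far as collection goes. It does not answer the reporting rule in Protocol 6.1 or the absence of any complaint table in the SAP.

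A second reply is that the wording about administration only places the form in the Day 1 sequence, where Appendix D lists it as a required activity, and that an investigator might mention a failed first device on it. The form's items are not shown, so this cannot be excluded. Nothing requires it, however.

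Third, the procedure steps are weak evidence about retention. Step 7 concerns dropping the device, step 12 concerns needle damage, and neither tests the retention feature. That is fair. They show only that an opened device can be set aside before injection.

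A reader might go further and infer three things that the documents do not support:

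- *The subject is counted as a success on a replacement device.* No replacement is described and no success criterion is defined.
- *A planned success rate is biased upward.* No such rate, interval or comparison is planned; there is no hypothesis, and the form is only to be summarised.
- *The study is blind to retention failures.* An implant lost unnoticed before injection would still be a non-delivery on the form, which asks about exactly that. Ophthalmoscopy after the procedure supports the answer, although the manual notes that the implant is not always visible at once. Only failures noticed and rejected before injection are missed.

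**Conclusion.** The point holds as a gap in linkage and reporting. Followed as written, the plan would collect failures before injection as complaints and then leave those without an adverse event out of the reported evidence on the sole objective, for both applicators and whether or not a second kit is used. In an arm of 36, each omitted device is worth a little under 3 percentage points, and the first lowers the exact lower limit from 90.3% to 85.8%. That size rests on assumed counts and on all treated subjects having a favourable form. If no applicator is rejected before injection, nothing changes. The documents do not show that any rejection will occur or that a biased rate will be published.

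**What to change.** - **Protocol 3.4 and Operations Manual 3.13:** for every applicator opened for a subject, require either an assessment form or a linked Product Complaint eCRF record. It should hold the kit number, applicator type, stage of any failure and whether the device entered the eye.
- **Protocol 6.1 and the SAP:** report all product complaints by applicator type, not only those with an adverse event.
- **SAP:** add the form summary that Protocol 7.5 promises, by applicator type, and beside it give applicators that delivered divided by applicators opened. A second applicator in the same subject counts as its own record. The subject-level safety tables stay as they are.

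How a rejected applicator is handled, and whether another is issued, is for the sponsor to specify; the record should work in either case.

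The cost is slightly more data entry, a few sentences and one extra table. Using the linked complaint record avoids entering the same failure twice. The delivered share can only stay the same or become slightly less favourable than one based on treated subjects alone.

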2 INTRODUCTION

2.1 Background and Rationale

Why Is This Study Being Conducted?

Dexamethasone Posterior Segment Drug Delivery System (DEX PS DDS) is a Food and Drug Administration (FDA)-approved, biodegradable, NOVADUR® solid polymer drug delivery system containing 0.7 mg of dexamethasone. The DEX PS DDS Implant comes preloaded and is delivered in the vitreous cavity by a single-use DEX PS DDS Applicator with a 22 gauge needle that leaves a sutureless self-sealing wound. The sustained release formulation was designed to release dexamethasone from the DEX PS DDS Implant for up to 6 months into the posterior segment of the eye. The DEX PS DDS is approved for the treatment of macular edema following branch retinal vein occlusion (BRVO) or central retinal vein occlusion (CRVO), for the treatment of noninfectious uveitis affecting the posterior segment of the eye, and for the treatment of diabetic macular edema (DME).

AbbVie is updating the DEX PS DDS Applicator to include a change of the implant retention feature, other minor changes to the DEX PS DDS Applicator (i.e., change of safety tab color, shortening of the safety tab, linkage hole alignment, lever clasp), as well as the change to the visual/physical depth of penetration feature (needle sleeve).

There is no defined clinical hypothesis for this study. This study is designed to demonstrate that the updated DEX PS DDS Applicator (that incorporates the final, to be-marketed design) delivers the DEX PS DDS Implant to the vitreous cavity and is suitable for commercial use in patients with macular edema due to retinal diseases. No changes are being made to the DEX PS DDS Implant. As the safety of the DEX PS DDS Implant is already well characterized and is the same as the currently marketed product, the duration of the proposed study is designed to capture investigator experience and any complaints associated with the DEX PS DDS Implant administration using the updated DEX PS DDS Applicator. The planned assessments include best-corrected visual acuity (BCVA), biomicroscopic slit lamp examination, ophthalmoscopy, and intraocular pressure (IOP). Adverse events (AEs) will also be collected. The treatment administration assessment form will be collected to evaluate investigator experience with and performance of the updated DEX PS DDS Applicator and the currently-approved DEX-PS DDS Applicator as a comparator. These parameters are sufficient to determine whether the updated DEX PS DDS Applicator delivers the DEX PS DDS Implant to the vitreous cavity.

2.2 Benefits and Risks to Subjects

The DEX PS DDS Implant was developed to address the problems associated with conventional corticosteroid therapies. The DEX PS DDS Implant administered into the posterior segment of the eye releases a total dose of approximately 0.7 mg dexamethasone. Other routes of administration (topical, periocular, systemic, and standard intravitreal injection of corticosteroid suspensions) require much higher daily doses to deliver equivalent levels of corticosteroid to the posterior segment while also exposing non-target organs to corticosteroids. With DEX PS DDS Implant, substantially lower daily doses of dexamethasone are released directly to the posterior segment, thereby minimizing potential systemic side effects. The DEX PS DDS Implant gradually degrades over time while releasing dexamethasone until it ultimately disappears from the vitreous. Therefore, there is no need to remove the DEX PS DDS

Implant. By delivering a drug directly into the vitreous cavity, the blood-eye barriers are circumvented, and intraocular therapeutic levels can be achieved with minimal risk of systemic toxicity.

The updates being evaluated in this study are related to the DEX PS DDS Applicator only; the DEX PS DDS Implant remains unchanged. The safety of the DEX PS DDS Implant is already well characterized and is the same as the currently marketed product.

Based on the information mentioned above, no additional or new risks are anticipated other than those previously known for DEX PS DDS Implant.

For further details, please see findings from completed studies, including safety data in the current DEX PS DDS investigator's brochure.

Considering the Coronavirus Disease – 2019 (COVID-19) pandemic, the benefit and risk to subjects participating in this study have been re-evaluated. Based on the limited information to date, and given the minimal systemic exposure to the active ingredient, no additional risk to study subjects is anticipated with the use of DEX PS DDS Implant.

